10.1. Visit 5a

Subjects will provide written informed consent and then will be evaluated with respect to the inclusion/exclusion criteria. Assessments conducted at Visit 5 of Study OTX-101-2016-001 are not repeated.

If Visit 5a is not conducted on the same day as Visit 5 of Study OTX-101-2016-001, the following procedures will be conducted.

- AE assessment
- Concomitant medication review
- Urine pregnancy test (women of childbearing potential only)

Subjects who meet all inclusion/exclusion criteria will be assigned a kit of study medication and are again instructed in topical ocular drop administration procedures.

- Dispense study medication

10.2. Treatment Visits

10.2.1. Visit 6 (Day 182), Visit 7 (Day 273) and Visit 8 (Day 364)*

Procedures performed on Days 128 (± 7 days), 273 (± 7 days) and 364* (± 14 days) will include the following:

- AE assessment
- Concomitant medication review
- Urine pregnancy test (women of childbearing potential only)
- Corrected Snellen VA
- Slit lamp examination
- IOP
- Collect and document used and unopened study medication materials
- Dispense study medication

* If not the final visit

10.3. Final Study Visit: Visit 8 (Day 364) or Visit 9 (Day 448)

Procedures performed at the subject's final visit; i.e., Day 364 (+14 days) or Day 448 (+14 days), depending on their treatment assignment in Study OTX-101-2016-001, will include the following:

- Collect and document used and unopened study medication materials
- AE assessment
- Concomitant medication review
- Urine pregnancy test (women of childbearing potential only)
- Corrected Snellen VA
- Slit lamp examination
- IOP
- Ophthalmoscopy/dilated fundus examination

10.4. Telephone Contact

The subject will be contacted by telephone approximately midway between scheduled visits (i.e., Days 227, 318 and 409) to assess the following:

- AE assessment
- Concomitant medication review

10.5. Early Discontinuation Visit

If the subject is discontinuing the study early, procedures performed will include the following:

- Collect and document all used and unopened study medication materials, if available; otherwise arrange for the subject to return them
- AE assessment
- Concomitant medication review
- Urine pregnancy test (women of childbearing potential only)
- Corrected Snellen VA
- Slit lamp examination
- IOP
- Ophthalmoscopy/dilated fundus examination

11. STATISTICS

11.1. General Considerations

This is an extension of Protocol OTX-101-2016-001 that will evaluate the safety of OTX-101 0.09% ophthalmic solution in subjects with KCS when dosed twice per day for one year.

Subjects in Protocol OTX-101-2016-001 were randomly assigned to OTX-101 0.09% or its vehicle in a 1:1 ratio. However, all subjects enrolling in this extension study will be assigned to OTX-101 0.09%.

A biostatistician will perform statistical analyses as agreed with the Sponsor according to the Statistical Analysis Plan. Any additional or supplemental data analysis performed independently by an Investigator shall be submitted to the Sponsor for review.

No efficacy analyses will be performed. Safety analyses will be performed using the safety analysis population. Definitions for all of the analysis populations can be found in Section 11.5.

11.2. Definition of Baseline Measurements

Baseline measurements will be the last measurement for the corresponding variable prior to the first randomized dose on Day 0 of Protocol OTX-101-2016-001.

11.3. Handling of Missing Data

No missing efficacy data will be imputed. The reasons for missing data will be recorded.

11.4. Determination of Sample Size

In accordance with the ICH E1A Guidance, safety data for a minimum of 100 subjects treated for one year is recommended for inclusion in applications for marketing approval. The masking of subject treatment assignments in Study OTX-101-2016-001 will be maintained until the database for that study has been locked, so qualified subjects receiving OTX-101 0.09% or vehicle may be enrolled in Study OTX-101-2016-002. Approximately [REDACTED] subjects will enroll in Study OTX-101-2016-002 of which it is anticipated that at least [REDACTED] will have been randomly assigned to OTX-101 0.09% in Study OTX-101-2016-001.

11.5. Analysis Populations

Two populations will be used for analysis.

11.5.1. Safety Analysis Populations

The safety population will include all patients enrolled in Study OTX-101-2016-002 who have received at least one dose of the study medication.

11.5.1.1. One Year Safety Population

Certain analyses will include only those subjects with a total of 1 year of exposure to active drug in Studies OTX-101-2016-001 and OTX-101-2016-002. The combined safety data from both protocols will be analyzed for this population.

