11.8. Safety Analyses

Safety and tolerability data will be presented in tables of descriptive statistics and frequency distribution. All summary tables will be supported with individual subject data listings. For all subjects enrolled in Study OTX-101-2016-002, the safety data recorded during Study OTX-101-2016-001 will be merged to produce a dataset encompassing one year of exposure to treatment.

AEs that occurred during the run-in period on vehicle of Protocol OTX-101-2016-001 will be summarized separately from AEs that occur from the first dose of double-masked treatment on Day 0 of that protocol to the Day 364 or Day 448 visit of Protocol OTX-101-2016-002.

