## **5. ANALYSIS POPULATIONS**

Three populations will be used for analysis.

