### **5.1. Safety Analysis Populations**

The safety population will include all patients who were enrolled in Study OTX-101-2016-002 and received at least one dose of the study medication.

Summaries will be presented by the following groups of subjects:

1. subjects assigned to the OTX-101 0.09% arm in Study OTX-101-2016-001; i.e., those subjects with 12 months exposure to active drug.
2. subjects assigned to the Vehicle arm in Study OTX-101-2016-001; i.e., those subjects with at least 9 months of exposure to active drug.

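### The protocol's one-year safety set excludes early AE stoppers by definition, and the SAP neither withdraws it nor plans an all-dosed combined one-year AE result

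*Protocol*

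**What the plan says.** Protocol 11.5 names two populations. The first is all-inclusive (11.5.1): "The safety population will include all patients enrolled in Study OTX-101-2016-002 who have received at least one dose of the study medication". The second is the One Year Safety Population (11.5.1.1): "Certain analyses will include only those subjects with a total of 1 year of exposure to active drug", followed by "The combined safety data from both protocols will be analyzed for this population". The analyses are not listed, one year is not given in days, and the set is not called supportive.

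Elsewhere the protocol points to the all-dosed set. Section 11.1 says "Safety analyses will be performed using the safety analysis population". Section 11.8 says "For all subjects enrolled in Study OTX-101-2016-002, the safety data recorded during Study OTX-101-2016-001 will be merged", and there the AE summary runs from Day 0 of Study 001 to the final extension visit.

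SAP 5 opens with "Three populations will be used for analysis", but SAP 5.1 defines one: "The safety population will include all patients who were enrolled in Study OTX-101-2016-002 and received at least one dose of the study medication". That population is shown in two groups by Study 001 arm, and the prior-active group is described as "those subjects with 12 months exposure to active drug". SAP 7.6 counts an AE as treatment-emergent from the first OTX-101 dose in Study 002, or if an earlier event worsens after that dose. SAP 8 reports no changes from the protocol.

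**The concern.** Membership of the one-year set depends on something that happens after treatment starts, namely staying on drug for a year. Stopping for intolerance is one of the safety outcomes of interest, and it removes the subject from the analysis. The study's only objective is long-term safety, so a table headed as the one-year result could be read as the answer to that objective while leaving out the subjects who tolerated the drug least.

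The SAP does not settle the matter. It leaves the set in force (no changes declared, an unexplained third population) without saying which analyses use it, so that choice could be made after the data are seen. It also lists no all-dosed table of combined-study AEs, which would make the completer set unnecessary. Finally, describing the prior-active group by 12 months of exposure, when membership is by assignment, invites the reader to treat early stoppers as if they had a full year.

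**Working it through.** **1. The plan's own figure.** SAP 4 expects about 300 subjects, at least 150 of them prior-active. With the 1:1 allocation in Protocol 11.1, 300 × 1/2 = 150, which reproduces. The 100-subject one-year target needs 100/150 = 66.7% of that group to reach a year. This is a count, and it is a sound use for a one-year set.

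**2. Who can be in the set.** Scheduled active exposure from the Schedule of Procedures:
- Prior-active: 84 + 280 = 364 days at Visit 8.
- Prior-vehicle: 280 days at Visit 8, or 448 − 84 = 364 days at Visit 9.

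The set therefore drops everyone who stops before a year, including AE stoppers. It also drops prior-vehicle subjects who leave at Visit 8, for reasons that need not involve safety. Protocol 11.5.1.1 gives no day count; the top exposure category in SAP 7.5 starts at 360 days.

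**3. Effect on AE rates.** Let d be the share of dosed subjects who stop for an AE before one year, and p the any-AE rate in everyone else. Assume that subjects who stop for other reasons also have rate p.
- AE discontinuation before one year: d in all dosed subjects, 0 in the one-year set.
- Any AE: d + (1 − d)p in all dosed subjects, p in the one-year set. The difference is d(1 − p).

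The documents give neither d nor p for one year. Over assumed ranges:

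| d | all-dosed rate if p = 20% | all-dosed rate if p = 40% | understatement (points) |
|---|---|---|---|
| 2% | 21.6% | 41.2% | 1.6 / 1.2 |
| 5% | 24% | 43% | 4 / 3 |
| 10% | 28% | 46% | 8 / 6 |
| 15% | 32% | 49% | 12 / 9 |

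Subjects who stop for other reasons are observed for less time and may have fewer recorded AEs, which would narrow the any-AE gap. The zero for AE discontinuation does not depend on this.

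**4. An illustrative d.** Protocol 4.4 reports 3 drug-related AE discontinuations on 0.09% in the 12-week Phase 2b study. The arm size is not stated. Of the values 145 to 159, only 152 fits that arm's percentages (23/152 = 15.1%, 3/152 = 2.0%, 30/152 = 19.7%), so 152 is assumed.
- 3/152 = 1.97%; exact 95% interval 0.41% to 5.66%.
- Prior-active entrants have already completed Study 001 (inclusion criterion 1), so 40 weeks remain at risk.
- At a constant hazard: 1 − (1 − 0.0197)^(40/12) = 6.4%. The interval ends give 1.4% and 17.7%.

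SAP 9 gives 258 enrolled and exposed subjects but no split by Study 001 arm, so no head count is offered.

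**5. What the SAP tables cover.** Tables 14.3.1.1 to 14.3.1.5, including the table of AEs leading to permanent withdrawal, are on the Safety Population. No listed table uses a one-year set. Under SAP 7.6, a prior-active subject's AE during the 12 weeks on OTX-101 in Study 001 does not count unless it worsens later. Those tables thus cover about 40 scheduled weeks for prior-active subjects and up to 52 for prior-vehicle subjects, as counts and percentages only. The merged all-enrolled AE summary of Protocol 11.8 has no identifiable SAP table.

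**The case against.** The strongest reply is that early stoppers are already counted. The all-dosed population is the one Protocol 11.1 assigns to safety analyses, Protocol 11.8 merges data for all enrolled subjects, and every AE table in SAP 10 with a population label uses the Safety Population. SAP 7.1 summarises reasons for discontinuation for all subjects, and the interim subset in SAP 9 kept premature discontinuations. This stands. A reader might infer from Protocol 11.5.1.1 that the trial's AE reporting as a whole is restricted to completers; the documents do not support that.

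It is also fair to say that no planned table presents a completer-only AE rate, and that the protocol does not name AE incidence among the analyses on the one-year set. This limits the harm but does not remove the rule. Combined safety data are to be analysed in that set, and the SAP declares no departure.

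The mismatch in the number of populations and the 12-month label remove nobody from a denominator, and SAP 7.5 tabulates actual exposure. They are alignment and labelling faults, not evidence of bias. They matter because they leave the status of the one-year set open.

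On size, a reader might extrapolate the Phase 2b rate over 52 weeks and reach 8.3%. That charges prior-active subjects with 12 weeks they must already have completed to enter. Even the 40-week figure rests on three events and an unverified hazard; stops concentrated early in treatment would lower it.

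**Conclusion.** The point holds for the supplementary one-year analyses and for the gap the SAP leaves around them. In the one-year set, AE discontinuation before one year is zero by definition, and other AE rates tend to be understated, by 1.2 to 12 points over the assumed ranges of d and p. The main AE tables are sound in their denominator. For prior-active subjects, however, they do not give a combined one-year result, because event counting restarts at the first Study 002 dose.

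The documents do not determine the actual size of the bias. The 6.4% (1.4% to 17.7%) is an illustration that assumes 152 subjects in the Phase 2b arm, a constant hazard, and the same drug-related stopping rate in subjects who already completed Study 001. The zero rate rests on none of these assumptions.

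**What to change.** - **Protocol 11.5.1.1:** use the one-year set only to count subjects against the 100-subject exposure target, and state the day count for one year. The top exposure category in SAP 7.5 could serve, if that section says that exposure runs from the first OTX-101 dose in either study.
- **SAP 7.6 and 10:** add the combined-study AE and AE-discontinuation summary of Protocol 11.8 for all enrolled and dosed extension subjects. Keep events on vehicle in Study 001 separate from events on OTX-101.
- **Rates:** because the cohorts are scheduled for different extension lengths (40 versus up to 52 weeks), add exposure-adjusted rates or Kaplan-Meier incidence by Study 001 arm.
- **SAP 5.1:** label the groups by Study 001 arm, not by months of exposure.
- **Protocol 11.5 and SAP 5 and 8:** agree on the number and definition of populations, and record any departure from the protocol.

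The cost is some lines of text and one or two extra tables. The one-year AE figures would probably be slightly less favourable than those from the completer set.

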11.6. Demographics and Baseline Characteristics

Subject demographic and baseline characteristics will be summarized for the safety analysis populations. Summary tables will be supported with individual subject data listings.

11.7. Efficacy Analysis

Not applicable

11.7.1. Hypothesis Testing

Not Applicable

11.8. Safety Analyses

Safety and tolerability data will be presented in tables of descriptive statistics and frequency distribution. All summary tables will be supported with individual subject data listings. For all subjects enrolled in Study OTX-101-2016-002, the safety data recorded during Study OTX-101-2016-001 will be merged to produce a dataset encompassing one year of exposure to treatment.

AEs that occurred during the run-in period on vehicle of Protocol OTX-101-2016-001 will be summarized separately from AEs that occur from the first dose of double-masked treatment on Day 0 of that protocol to the Day 364 or Day 448 visit of Protocol OTX-101-2016-002.

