
Methodology: This is an open-label extension of OTX-101-2016-001, a randomized, multicenter, double-masked, vehicle-controlled study in which subjects were randomized to 1 of 2 treatment arms and treated for 12 weeks as follows:
 
 • OTX-101 0.09% (N = ■■■ subjects) • Vehicle (N = ■■■ subjects) 
Subjects successfully completing Study OTX-101-2016-001 may be eligible to enroll in this 40 to 52 week open label extension study in which all subjects will receive OTX-101 0.09% therapy. Subjects may also use unpreserved artificial tears, as needed. Subjects assigned to OTX-101 0.09% in Study OTX-101-2016-001 will participate for 40 weeks. Subjects assigned to vehicle in Study OTX-101-2016-001 are eligible to participate for 52 weeks. Both subject sets will total 52 weeks of participation receiving OTX-101 0.09%.
 
Subjects may enroll in Study OTX-101-2016-002 for up to 14 days following completion of Visit 5 of Study OTX-101-2016-001. At Visit 5a, sites will obtain signed informed consent and dispense study medication. If Visit 5a is not conducted on the same day as Visit 5 of Study OTX-101-2016-001, any female subject of childbearing potential must also have a negative urine pregnancy test. Study “Day” approximately reflects the cumulative number of days of exposure to study drug since the baseline visit of Protocol OTX-101-2016-001, regardless of actual calendar time elapsed.
 
Subjects will self-administer study medication topically to both eyes BID for 40 to 52 weeks depending on their treatment assignment in Study OTX-101-2016-001. Safety evaluations for all subjects will be conducted at study visits on Days 182, 273 and 364; the window for Visits 6 (Day 182) and Visit 7 (Day 273) will be ± 7 days; the window for Visit 8 (Day 364) will be +14 days for those subjects assigned to OTX-101 0.09% in Study OTX-101-2016-001. (± 14 days for subjects assigned to vehicle in Study OTX-101-2016-001, participating for 52 weeks in Study OTX-101-2016-002). Subjects assigned to vehicle in Study OTX-101-2016-001, participating for 52 weeks in Study OTX-101-2016-002, will also be evaluated at Visit 9 (Day 448), which will have a visit window of +14 days. Both eyes will be assessed at each visit. Adverse events and concomitant medications will be documented from signing of informed consent to the subject’s final visit.
	

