6. INVESTIGATIONAL PLAN

6.1. Overall Study Design

This will be an extension of OTX-101-2016-001, a randomized, multicenter, double-masked, vehicle-controlled study that enrolled male and female subjects, 18 years of age and older, with a patient-reported history of KCS for a period of at least 6 months, a clinical diagnosis of bilateral KCS supported by OTX-101-2016-001 study assessments, and corrected Snellen VA of better than 20/200 in both eyes at Screening and at Baseline.

Subjects who complete Visit 5 (Day 84) of Study OTX-101-2016-001 may be eligible to enroll in protocol OTX-101-2016-002 within 14 days at the discretion of the Principal Investigator and Sponsor. Subjects who provide written informed consent at Visit 5a and meet the inclusion/exclusion criteria requirements will be enrolled in the study and receive study medication (OTX-101 0.09%). All subjects will participate for at least 40 weeks. Subjects who were randomized to the vehicle arm in Study OTX-101-2016-001 may have the opportunity to participate for additional 12 weeks, total of 52 weeks.

Subjects will self-administer study medication topically to both eyes BID from Visit 5a to Visit 8 (Day 364) or Visit 9 (Day 448). Safety evaluations will be conducted at all study visits. The window for Visits 6 and 7 will be ± 7 days. The window for Visit 8 will be +14 days for those subjects assigned to OTX-101 0.09% in Study OTX-101-2016-001 (± 14 days for subjects assigned to vehicle in Study OTX-101-2016-001, participating for 52 weeks in Study OTX-101-2016-002), and Visit 9 will be +14 days. Both eyes will be assessed at each visit. Adverse events and concomitant medications will be documented from signing of informed consent at each study visit.

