### **Definition of Baseline:**

Baseline measurements will be the last measurement for the corresponding variable prior to the first dose of OTX-101 0.09%. For those initially randomized to OTX-101 0.09%, baseline would be the day of randomization (Day 0). For those initially randomized to Vehicle, baseline would be the day of the first dose of OTX-101 0.09% in the extension phase.

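### Protocol and SAP start the AE window, baseline and exposure at different points; neither gives a correct OTX-101 window for both former arms, and SAP 8 declares no change

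*Protocol*

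**What the plan says.** **Protocol.** The synopsis states that in Study 001 "subjects were randomized to 1 of 2 treatment arms and treated for 12 weeks as follows", the arms being OTX-101 0.09% and vehicle. Section 11.1 adds: "Subjects in Protocol OTX-101-2016-001 were randomly assigned to OTX-101 0.09% or its vehicle in a 1:1 ratio". Section 6.1 says that former vehicle subjects "may have the opportunity to participate for additional 12 weeks", so their record ends at Visit 8 (Day 364) or Visit 9 (Day 448).

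For all Study 002 subjects, section 11.8 says that "the safety data recorded during Study OTX-101-2016-001 will be merged to produce a dataset encompassing one year of exposure to treatment". It keeps run-in vehicle AEs apart from "AEs that occur from the first dose of double-masked treatment on Day 0 of that protocol to the Day 364 or Day 448 visit", where the protocol referred to is Study 001. It gives no split by Study 001 arm and does not set the 12 randomised-vehicle weeks apart. Section 11.2 takes baseline for every subject as the last measurement "prior to the first randomized dose on Day 0 of Protocol OTX-101-2016-001". Section 11.5.1.1 limits certain analyses to subjects with a year on active drug, but still uses the combined data of both studies.

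**SAP.** Section 7 sets another baseline: "For those initially randomized to Vehicle, baseline would be the day of the first dose of OTX-101 0.09% in the extension phase". Section 7.6 starts TEAEs at the first OTX-101 dose in Study 002 for both former arms, and adds earlier events that worsen after it. Section 5.1 presents results by former arm and describes the former OTX-101 group as having 12 months on active drug. Section 7.5 computes exposure as last minus first dosing date plus one, without naming the study. Section 8 declares no changes from the protocol.

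**The concern.** The only objective is the long-term safety of OTX-101 0.09%, so the start of the observation window determines what the main output measures. For a former vehicle subject, the first double-masked dose was vehicle. A summary built to Protocol 11.8 without a further split would mix vehicle and OTX-101 time. Under Protocol 11.2, the same subject's change in visual acuity or IOP would span both periods. The two exposures are not interchangeable: the Phase 2b results in Protocol 4.4 give drug-related events in 19.7% of subjects on 0.09% and 7.9% on vehicle.

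The SAP avoids this for former vehicle subjects but opens the opposite gap. Former OTX-101 subjects lose their first 12 active weeks from the TEAE window, although their description as a 12-month group depends on those weeks. With SAP 8 silent, a programmer or assessor cannot tell which rule is intended.

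**Working it through.** **Inputs.** Study 001 treatment: Day 0 to Day 84 (12 weeks). Visit 8: Day 364. Visit 9: Day 448. All are in the protocol's synopsis and schedule. The days below are nominal; the visit windows and the plus one in SAP 7.5 are ignored unless stated.

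**1. The plan's own figure.** The synopsis plans 52 weeks on OTX-101 for both sets.
- Former OTX-101: 84/7 + (364 − 84)/7 = 12 + 40 = 52 weeks.
- Former vehicle to Visit 9: (448 − 84)/7 = 52 weeks.

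Both reproduce. A former vehicle subject who stops at Visit 8 has (364 − 84)/7 = 40 active weeks.

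**2. Vehicle time in the Protocol 11.8 window, per former vehicle subject.**
- To Day 448: 64 weeks, of which 52 active and 12 vehicle; 84/448 = 18.75%.
- To Day 364: 52 weeks, of which 40 active and 12 vehicle; 84/364 = 23.1%.

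Neither record is one year of OTX-101 alone.

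**3. Vehicle share of the whole merged dataset.** Assume equal former arms and full follow-up.
- All former vehicle subjects to Day 448: 12/(52 + 64) = 10.3%.
- All former vehicle subjects to Day 364: 12/(52 + 52) = 11.5%.

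These shares do not depend on the number enrolled. They apply only to the Protocol 11.8 window.

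**4. Active time left out by SAP 7.6, per former OTX-101 subject.** The TEAE window covers 364 − 84 = 280 of 364 active days. The part left out is 84/364 = 23.1%. SAP 4 anticipates at least 150 such subjects among about 300.

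**5. Exposure under SAP 7.5, by starting date (days).**

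| Subject | First Study 001 dose | First Study 002 dose | First OTX-101 dose |
|---|---|---|---|
| Former OTX-101, to Visit 8 | 364 | 280 | 364 |
| Former vehicle, to Visit 8 | 364 | 280 | 280 |
| Former vehicle, to Visit 9 | 448 | 364 | 364 |

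The top category in SAP 7.5 begins at 360 days. From the first Study 001 dose, a former vehicle subject stopping at Visit 8 falls in that category with only 280 active days. From the first Study 002 dose, a former OTX-101 subject reaches about 280 days, or 280 + 14 = 294 at the edge of the Visit 8 window, so none reaches 360. Only the third column agrees with SAP 5.1 for both groups.

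**6. Rules side by side.**

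| Item | Protocol | SAP |
|---|---|---|
| AE start, former OTX-101 | Study 001 Day 0 | first Study 002 dose |
| AE start, former vehicle | Study 001 Day 0 | first Study 002 dose |
| Baseline, former vehicle | before Study 001 Day 0 | before first OTX-101 dose in the extension |
| Declared change | n/a | none |

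The protocol's AE start suits the former OTX-101 arm and the SAP's suits the former vehicle arm. Neither suits both.

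**The case against.** The strongest reply is that the planned analysis does not do what Protocol 11.8 seems to invite. Protocol 11.1 hands the analysis to the SAP. There, TEAEs start at the first Study 002 dose, tables are by former arm, the vehicle-arm baseline is reset, and visual acuity and IOP tables show only extension visits plus that baseline. The SAP's table list has no table that merges AEs from Study 001 Day 0. All of this stands.

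A reader might infer from 11.8 that vehicle weeks are to be reported as OTX-101 experience. The documents do not support that. The text says treatment, not OTX-101; merging data does not rule out display by arm or period; and section 11.5.1.1 names active drug where it means active drug. The defect in 11.8 is that it is silent about the randomised-vehicle weeks.

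A reader might also apply the Phase 2b vehicle rate of 7.9% to half of the 258 enrolled (129 × 0.079, about 10) and expect that many former vehicle subjects to carry a vehicle-period event into the results. That does not describe the operative analysis, whose TEAE tables exclude AEs confined to that period. It also applies a rate from all Phase 2b subjects to people selected for completing Study 001, and the SAP gives no arm split of the 258.

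The reply does not remove the undeclared conflict, the 12 active weeks dropped by SAP 7.6, or the ambiguity in SAP 7.5.

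**Conclusion.** The point holds as a conflict between the protocol and the SAP that leaves no correct OTX-101 window for both groups. Under Protocol 11.8, each former vehicle subject contributes 12 vehicle weeks (18.75% or 23.1% of the record) to a dataset labelled as one year of exposure. Under SAP 7.6, each former OTX-101 subject loses 12 active weeks (23.1%). SAP 8 is wrong to declare no change.

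The per-subject figures rest on nominal visit days and completed follow-up. The 10.3% share of merged follow-up also needs equal former arms and every former vehicle subject reaching Day 448, although the last 12 weeks are optional. The documents do not allow an estimate of how many AEs are affected. The direction is clear for the percentage of subjects with an AE: adding the omitted active weeks can raise it or leave it unchanged, but cannot lower it.

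**What to change.** 1. In SAP 7.5 and 7.6, start exposure and the AE window at each subject's first OTX-101 dose in either study: Study 001 Day 0 for the former OTX-101 arm, and the first extension dose for the former vehicle arm. State how the interval of up to 14 days between Visits 5 and 5a is counted.
2. Keep summaries by former arm, and show AEs from the randomised-vehicle period separately, as Protocol 11.8 already does for the run-in.
3. Keep the SAP 7 baseline. Say that for the former vehicle arm it means Visit 5 values, since Protocol 10.1 does not repeat those assessments at Visit 5a.
4. In SAP 8, list the departures from Protocol 11.2 and 11.8 that remain. If the protocol is amended for other reasons, align those two sections and shorten the list accordingly.

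The cost is SAP wording and one date-based split in the AE programming. SAP 9 already counts total OTX-101 exposure across the two studies, so the dates should be in hand. AE counts for the former OTX-101 group may rise somewhat. A protocol amendment would cost more, because Protocol 13.7 requires submission to the FDA and IRB approval before implementation; the SAP changes can be made without it.
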